7.3. Blinding

Blinding will be determined for the specific investigation in each addendum.

7.4. Dose Modification

Refer to each addendum for specific dose modification instructions.

7.5. Preparation/Handling/Storage/Accountability

Investigators should consult the study drug information provided in the Pharmacy Manual or label for the specific addendum for administration information (including warnings, precautions, contraindications, adverse reactions, and dose modifications).

7.6. Treatment Compliance

For an addendum in which study drug is administered by site personnel:

Study medication that is administered intravenously will be administered only at the investigational sites by the authorized study site personnel. As a result, treatment compliance is ensured.

For an addendum in which study drug is not administered by site personnel:

Patient compliance with study medication that is not administered by site personnel will be assessed as described in the specific addendum. Deviations from the prescribed dosage regimen should be recorded in the patient's record.

A patient will be considered significantly noncompliant if he or she is judged by the investigator to have intentionally or repeatedly taken more or less than the prescribed amount of medication. The threshold required to maintain status as compliant will be at least 80% unless otherwise specified in Section 3.6.5 of the specifically enrolled addendum.

Potential discontinuation of a patient due to study drug noncompliance will be discussed between the investigator and the Lilly CRP/CRS before the final determination is made to discontinue the patient from the study.

7.7. Concomitant Therapy

All concomitant medications should be recorded throughout the patient's participation in the study.

Concomitant medications and supportive care therapies must also be documented at the time of discontinuation and at the short-term follow-up visit.

Appropriate documentation for all forms of premedications, concomitant medications, and supportive care (for example, medications such as sedatives, antibiotics, analgesics, antihistamines, corticosteroids, erythropoietin; procedures such as paracentesis, thoracentesis; or blood products such as blood cells, platelets, or fresh frozen plasma transfusions) must be captured on the electronic case report form (eCRF).

[figure not shown]
No other chemotherapy, investigational medications, other anticancer therapy, immunotherapy, hormonal cancer therapy, palliative radiation, or palliative surgery for cancer will be permitted while patients are on study treatment. Radiation and surgery for cancer (other than palliative) may be allowed after discussion with the Lilly CRP. Exceptions will be defined in each addendum.

A list of restricted and prohibited concomitant therapy is provided in the applicable specific addendum, Section 3.7.6.

7.8. Treatment after the End of the Study

The CAMPFIRE Master Protocol will reach the end of study when all addenda have been individually completed and no new addenda are planned. The end of the study for each investigation is the date of the last visit or last scheduled procedure shown in the Schedule of Activities (Section 3.2 in each addendum) for the last patient. Investigators will continue to follow the Schedule of Activities provided in the applicable protocol addendum until notified by Lilly that end of study for that investigation has occurred.

Refer to [Figure 7.1](#) for a depiction of these concepts per investigation: investigation completion, the continued-access period, and end of study.

^a Lilly will notify sites when the continued access period begins and ends.

^b Final analysis. Lilly will notify sites when completion of investigation occurs.

^c End of study occurs at the last visit or last scheduled procedure for the last patient.

Figure 7.1. Continued-access diagram for each investigation.

7.8.1. Treatment after Completion of Investigation

The completion of the investigation occurs following the final analysis, as defined in the applicable addenda and when determined by Lilly. Investigators will continue to follow the investigation-specific Schedule of Activities related to the study treatment period as outlined in the addenda for all patients until notified by Lilly that the completion of investigation has occurred. After that notification from Lilly, the investigation will enter the continued access period.

Several investigations (e.g. up to a total of approximately 10 investigations) will be added to the master protocol construct over approximately the next 5 years of the entire master protocol duration. These sub-protocols will be submitted and reviewed as independent clinical trial applications and will each include an estimation of the study duration.

7.8.1.1. Continued Access

Follow-up will be done as long as the patient is on treatment and participates in the trial.

After the final analysis of a given investigation-specific addendum has been conducted and Lilly has declared that the continued access period has begun, patients on that addendum who are still on study treatment may continue to receive study treatment if they are experiencing clinical benefit and no undue risks. Investigators will continue to follow the continued access Schedule

of Activities provided in the applicable protocol addendum for patients who remain on study treatment or in short-term follow-up during the continued access period.

The patient's continued access to study treatment will end when a criterion for discontinuation is met (Section 8). Continued access follow-up will begin when the patient and the investigator agree to discontinue study treatment, and lasts approximately 30 (± 7) days. Follow-up procedures will be performed as in the continued access Schedule of Activities shown in the applicable protocol addendum.

For patients who are in short-term follow-up during the study treatment period (as defined in the investigation-specific addendum) when the continued-access period begins, they will continue in short-term follow-up until the 30-day short-term follow-up visit is completed. Long-term follow-up during the study treatment period (as defined in the investigation-specific addendum) does not apply during the continued access period. Patients who are in long-term follow-up when the continued access period begins will be discontinued from long-term follow-up.

8. Discontinuation Criteria

8.1. Discontinuation from Study Treatment

Patients will be discontinued from study treatment in the following circumstances:

- The patient is enrolled in any other clinical study involving an investigational product or any other type of medical research judged not to be scientifically or medically compatible with this study.
- The patient becomes pregnant during the study.
- Investigator/Physician decision
 - the investigator/physician decides that the patient should be discontinued from the study or study drug(s)
 - if the patient, for any reason, requires treatment with another therapeutic agent that has been demonstrated to be effective for treatment of the study indication, discontinuation from the study drug(s) occurs prior to introduction of the other agent
- Patient, parent, or legal guardian decision
 - the patient or the patient's designee (for example, parents or legal guardian) requests to be discontinued from the study or study drug
- Sponsor decision
 - Lilly stops the study or stops the patient's participation in the study for medical, safety, regulatory, or other reasons consistent with applicable laws, regulations, and GCP
- The patient has radiographic progressive disease or significant symptomatic disease deterioration characterized as progression of disease, in the opinion of investigator, in the absence of radiographic evidence of PD. In the event a patient is discontinued from treatment due to symptomatic deterioration, every effort should be made to document disease progression, unless it is not medically appropriate.
- The patient experiences unacceptable toxicity (for example, a persistent moderate toxicity that is intolerable to the patient).
- The patient is noncompliant with study procedures and/or treatment (Section 7.6).
- The patient has had maximum dose reductions allowed per protocol and experiences an AE that would cause an additional dose reduction.
- Additional investigation-specific discontinuation criteria as shown in Section 3.8 of the addenda.

The reason and date of discontinuation will be collected for all patients. Patients who are discontinued from study treatment will have follow-up procedures performed as shown in the addendum-specific Schedule of Activities (Section 3.2).

8.1.1. Discontinuation of Inadvertently Enrolled Patients

The criteria for enrollment must be followed explicitly. If Lilly or the investigator identifies a patient who did not meet enrollment criteria and was inadvertently enrolled, a discussion must occur between the Lilly CRP/CRS and the investigator to determine if the patient may continue in the study, where local laws allow. If both agree, it is medically appropriate to continue, the investigator must obtain documented approval from the Lilly CRP/CRS to allow the inadvertently enrolled patient to continue in the study with or without study treatment. Patients who are discontinued from study treatment will have follow-up procedures performed as shown in the addendum-specific Schedule of Activities (Section 3.2).

8.2. Discontinuation from the Study

Patients will be discontinued from the specific addendum in the following circumstances:

- participation in the study needs to be stopped for medical, safety, regulatory, or other reasons consistent with applicable laws, regulations, and GCP
- the patient becomes pregnant during the specific addendum. See Section 9.2.1 regarding regulatory reporting requirements on fetal outcome
- the investigator decides that the patient should be discontinued from the study
- the patient requests to be discontinued from the specific addendum
- the patient's designee (legal representative) requests that the patient be discontinued from the specific addendum.

Patients who are discontinued from the specific addendum will have follow-up procedures performed as shown in the addendum-specific Schedule of Activities (Section 3.2).

8.3. Lost to Follow-Up

A patient will be considered lost to follow-up if he or she repeatedly fails to return for scheduled visits and is unable to be contacted by the study site. Study site personnel are expected to make diligent attempts to contact patients who fail to return for a scheduled visit or who the site is otherwise unable to follow-up.

9. Study Assessments and Procedures

Refer to the applicable protocol addendum for the schedule of activities, the schedule for collection of samples, and the list of laboratory tests.

Unless otherwise stated in the following subsections, all samples collected for specified laboratory tests will be destroyed within 60 days after receipt of confirmed test results. Certain samples may be retained for a longer period, if necessary, to comply with applicable laws, regulations, or laboratory certification standards.

9.1. Efficacy Assessments

Tumor assessments will be performed for each patient at the times shown in the schedule of activities and methods provided in the applicable protocol addendum.

Since radiographic imaging scans may be needed for an independent review or future regulatory purposes, copies of all scans will be collected throughout the study and stored centrally by a coordinating vendor designated by Lilly.

9.1.1. Appropriateness of Assessments

The measures used to assess efficacy and safety in this study are consistent with those most commonly used for the disease entities and therapeutic classes under investigation. See addenda for more detail.

9.1.2. Definitions of Efficacy Measures

Evaluation of efficacy measures may be primary, secondary, or exploratory endpoints of the CAMPFIRE Master Protocol's addenda. Included here are a list of common efficacy measures with standard definitions and general guidance for their use if adopted by an addendum.

Overall survival (OS) is defined as the time from enrollment until death from any cause. If the patient is alive or lost to follow-up at the time of data analysis, OS data will be censored on the last date the patient is known to be alive. Where applicable, the comparison of OS between treatment arms, as well as the corresponding hazard ratio (HR) estimator, will be described in each addendum. Overall survival curves, the median and survival rates at various time points with 95% CI, for each treatment arm will be estimated using the Kaplan-Meier method (Kaplan and Meier 1958). Sensitivity analyses for OS will be described in the addendum's SAP.

Progression-free survival (PFS) is defined as the time from enrollment until the first occurrence of documented disease progression per addenda-specified criteria, or death from any cause in the absence of PD. Patients known to be alive and without disease progression will be censored at the time of the last adequate tumor assessment.

Progression-free survival 2 (PFS2) is defined as the time from enrollment to disease progression (objective radiological or symptomatic progression) on the next line of treatment, or death from any cause in the absence of observed disease progression. If the patient is alive at the

cutoff for analysis, and disease progression after the first post-study treatment regimen has not been observed, PFS2 data will be censored on the last date the patient was known to be alive.

Objective response rate (ORR) is defined as the number of patients who achieve a best overall response of complete response (CR) or partial response (PR) divided by the total number of patients randomized to the corresponding treatment arm (intent-to-treat [ITT] population).

Duration of response (DoR) is defined as the time from the date that measurement criteria for CR or PR (whichever is first recorded) are first met until the first date that disease is recurrent or documented disease progression is observed, per addenda-specified criteria, or the date of death from any cause in the absence of documented disease progression or recurrence.

Disease control rate (DCR) is defined as the proportion of treated patients achieving a best overall response of PR or CR or stable disease (SD).

Clinical benefit rate (CBR): The proportion of patients with CR, PR, or SD \geq 6 months according to RECIST v1.1.

9.2. Adverse Events

The investigator will use Common Terminology Criteria for Adverse Events (CTCAE), Version 5.0 (NCI 2017) to assign AE severity grades.

Investigators are responsible for:

- monitoring the safety of patients in this study and for alerting Lilly or its designee to any event that seems unusual, even if this event may be considered an unanticipated benefit to the patient
- the appropriate medical care of patients during the study
- documenting their review of each laboratory safety report
- following, through an appropriate health care option, AEs that are serious or otherwise medically important, considered related to study treatment or the study, or that caused the patient to discontinue study treatment before completing the study. The patient should be followed until the event resolves, stabilizes with appropriate diagnostic evaluation, or is reasonably explained. Frequency of follow-up evaluation is left to the discretion of the investigator.

Lack of drug effect is not an AE in clinical studies, because the purpose of the clinical study is to establish treatment effect.

After the ICF is signed and assent obtained, as applicable, study site personnel will record via case report form (CRF) the occurrence and nature of each patient's preexisting conditions, including clinically significant signs and symptoms of the disease under treatment in the study. In addition, study site personnel will record via CRF any change in the preexisting conditions and any new conditions as AEs. Investigators should record their assessment of the potential relatedness of each AE to study procedure or study treatment via CRF.

The investigator will interpret and document whether or not an AE has a reasonable possibility of being related to study treatment or a study procedure, taking into account the disease, concomitant treatments, or pathologies. A “reasonable possibility” means that there is a cause-and-effect relationship between the study treatment and/or study procedure and the AE.

Adverse event grading of toxicities related to estimated GFR should be evaluated based on the Cockcroft-Gault method or measured GFR ([Appendix 4](#)).

Planned surgeries and nonsurgical interventions should not be reported as AEs unless the underlying medical condition has worsened during the course of the study.

Study site personnel must report any dose modifications or treatment discontinuations that result from AEs to Lilly or its designee via CRF/electronic data entry/designated data transmission methods, clarifying, if possible, the circumstances leading to the dose modification or discontinuation of treatment.

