
 • Synopsis • Introduction, including the master protocol rationale, and background information about unmet need in pediatric oncology • General inclusion and exclusion criteria • General Discontinuation criteria • Reporting of AEs, SAEs, and SUSARs • General assessment of efficacy, PK, genetics, and biomarkers • Data management methods • Study governance, regulatory requirements, and ethics, including informed consent/assent • List of references cited in the master protocol • List of abbreviations and definitions used in the master protocol 	
 • Investigation-specific synopsis • Background information about the investigation treatment(s) under evaluation, including the rationale for selection of tumor type(s) under investigation, the unmet medical need, and any accompanying investigation treatment(s) • Investigation-specific objectives, endpoints, study design, and statistical plan • Investigation-specific inclusion and exclusion criteria • Study drug administration and dosage modifications for agents under evaluation • Safety lead-in criteria and associated terms (if applicable) • Investigation-specific discontinuation criteria • AEs of special interest • Safety information specific to investigation treatment(s) and/or indication(s) under evaluation (if applicable) • Schedule of activities and schedule for collection of samples for PK, genetics, and biomarker research • Investigation-specific data management methods • List of restricted and prohibited concomitant therapy • List of references cited in the addendum • List of abbreviations and definitions used in the addendum

Abbreviations: AE = adverse event; PK = pharmacokinetics; SAE = serious adverse event; SUSAR = suspected, unexpected serious adverse reaction.

3. Introduction

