hematopoietic growth factors)	interferon, or cytokines (other than hematopoietic growth factors)
Antibody therapy	≥21 days after the last infusion of antibody therapy
Radiotherapy	≥ 14 days since local palliative radiation therapy (RT) (small port); craniospinal XRT, or 50% or greater pelvic radiation; ≥ 42 days for other substantial radiation (such as metaiodobenzylguanidine therapy)
Radiopharmaceutical therapy (eg, radiolabeled antibody, 131I-MIBG)	≥42 days after systemically administered radiopharmaceutical therapy
Stem cell infusion without TBI	≥84 days must have elapsed after auto-transplant or stem cell infusion
Corticosteroids	≥14 days for patients who have received a course of systemic corticosteroids (≥5 days) to modify immune AEs related to prior therapy. Note: Patients who are on chronic replacement dose for endocrine disorders or are on a stable or decreasing dose for indications other than treating the underlying cancer, may still be eligible (consult Lilly CRP/CRS)
Live vaccines	≥28 days after last live vaccine

[5] The patient has adequate hematologic and organ function ≤1 week (7 days) prior to first dose of study drug:

System	Laboratory Value
Hematologic	
ANC	$\geq 1000/\mu\text{L}$ G-CSF permitted up to 48 hours prior. Patients with documented history of benign ethnic neutropenia or other conditions could be considered with a lower ANC after discussion with and approval from the Lilly CRP/CRS
Platelets	$\geq 75,000/\text{mm}^3$ Platelet transfusion permitted up to 72 hours prior.
Hemoglobin	$\geq 8 \text{ g/dL}$ ($\geq 80 \text{ g/L}$) Transfusions to increase the patient’s hemoglobin level to at least 8 g/dL are permitted; however, study treatment must not begin until 7 days after the transfusion. and CBC criteria for eligibility are confirmed within 24 hr of C1D1
Hepatic	
Total bilirubin	$\leq 1.5 \times \text{ULN}$ Except patients with document history of Gilbert Syndrome who must have a total bilirubin level of $< 3.0 \times \text{ULN}$
ALT and AST	$\leq 2.5 \times \text{ULN}$ OR $\leq 5.0 \times \text{ULN}$ if the liver has tumor involvement

Abbreviations: ALT = alanine aminotransferase; ANC = absolute neutrophil count; AST = aspartate aminotransferase; CBC = complete blood count; ULN = upper limit of normal.

- Creatinine clearance or radioscope glomerular filtration rate (GFR) $\geq 60 \text{ mL/min/m}^2$ (Appendix 4) OR
- Serum creatinine meeting the following parameters:

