 - for patients ≥ 18 years of age serum creatinine $\leq 1.5 \times$ upper limit of normal (ULN);
 - for patients < 18 years of age, serum creatinine based on age/gender as follows:

Age	Maximum Serum Creatinine (mg/dL)	
	Male	Female
1 to < 2 years	0.6	0.6
2 to < 6 years	0.8	0.8
6 to < 10 years	1.0	1.0
10 to < 13 years	1.2	1.2
13 to < 16 years	1.5	1.4
16 to < 18 years	1.7	1.4

The threshold creatinine values in this table were derived from the Schwartz formula for estimating glomerular filtration rate (Appendix 4).

- [6] Female patients of childbearing potential must have a negative urine or serum pregnancy test within 7 days prior to Cycle 1 Day 1.
- [7] Both female and male patients of childbearing potential must agree to use highly effective contraceptive precautions during the trial and for at least 3 months following the last dose of study drug, or longer, if appropriate for other study drugs according to their label in order to prevent pregnancy.

Females of childbearing potential (FOCBP) and males who are abstinent (if this is complete abstinence, as their preferred and usual lifestyle) or in a same-sex relationship (as part of their preferred and usual lifestyle) must agree to either remain abstinent or stay in a same-sex relationship without sexual relationships with someone of the opposite sex. Periodic abstinence (e.g., calendar, ovulation, symptothermal, or postovulation methods), declaration of abstinence just for the duration of a trial, and withdrawal are not acceptable methods of contraception.

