10.3.1. Safety Analyses

The safety analyses are described below. Any additional safety analyses will be described in the addendum. In general, all patients who receive at least 1 dose of any study therapy will be evaluated for safety and toxicity.

The Medical Dictionary for Regulatory Activities (MedDRA[®]) Version 21 (or higher) will be used when reporting AEs. The MedDRA Lower Level Term (LLT) will be used in the

treatment-emergent computation. Treatment-emergent adverse events will be summarized by System Organ Class (SOC) and by decreasing frequency of Preferred Term (PT) within SOC.

Safety analyses will include summaries of the following:

- AEs, including severity and possible relationship to study drug
- SAEs, including possible relationship to study drug
- AEs leading to dose adjustments
- discontinuations from study treatment due to AEs or death
- treatment-emergent abnormal changes in laboratory values
- treatment-emergent abnormal changes in vital signs.

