Appendix 4. Creatinine Clearance Formula

Note: This formula is to be used for calculating creatinine clearance (CrCl) from **local laboratory results only**.

Patients ≥ 18 years old

Cockcroft-Gault prediction of creatinine clearance from serum creatinine (1976)

For serum creatinine concentration in mg/dL:

$$\text{CrCl} = \frac{(140 - \text{age}^a) \times (\text{wt}) \times 0.85 \text{ (if female), or } \times 1.0 \text{ (if male)}}{72 \times \text{serum creatinine (mg/dL)}} \text{ (mL/min)}$$

For serum creatinine concentration in $\mu\text{mol/L}$:

$$\text{CrCl} = \frac{(140 - \text{age}^a) \times (\text{wt}) \times 0.85 \text{ (if female), or } \times 1.0 \text{ (if male)}}{0.81 \times \text{serum creatinine } (\mu\text{mol/L})} \text{ (mL/min)}$$

^a Age in years, weight (wt) in kilograms.

Source: Cockcroft and Gault 1976.

-OR-

Patients < 18 years old will use the Schwartz formula for the determination of creatinine clearance.

All Females and Pre-adolescent Males:

$$C_{\text{cr}} \text{ (mL/min/1.73 m}^2\text{)} = 0.55 \times \text{Height (cm)} / S_{\text{cr}} \text{ (mg/dL)}$$

Adolescent Males:

$$C_{\text{cr}} \text{ (mL/min/1.73 m}^2\text{)} = 0.70 \times \text{Height (cm)} / S_{\text{cr}} \text{ (mg/dL)}$$

Note: C_{cr} = creatinine clearance and S_{cr} = serum creatinine.

Source: Schwartz et al. 1976; Schwartz and Gauthier 1985.

Appendix 5. Protocol Amendment J1S-MC-JAAA(b) Summary CAMPFIRE: Children's and Young Adult Master Protocol for Innovative Pediatric Research

Overview

Protocol J1S-MC-JAAA CAMPFIRE: Children's and Young Adult Master Protocol for Innovative Pediatric Research has been amended. The new protocol is indicated by amendment (b) and will be used to conduct the study in place of any preceding version of the protocol.

The overall changes and rationale for the changes made to this protocol are as follows:

- An inclusion criterion was added to clarify that age requirements will be specified in the protocol addenda
- Additional detail was added to the Benefit/Risk Assessment
- A current estimate of investigations to be added to the master protocol construct was added to Section 7.8.1

Revised Protocol Sections

Note: Deletions have been identified by strikethroughs . Additions have been identified by the use of underscore .
--

Section 3.3 Benefit/Risk Assessment

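### Section 9.2 grades estimated-GFR toxicities by Cockcroft-Gault at any age, but the Appendix 4 it cites assigns Schwartz to patients under 18, and 9.2 states no scale

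*Protocol*

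**What the plan says.** Section 9.2 (Adverse Events) sets the grading system: "The investigator will use Common Terminology Criteria for Adverse Events (CTCAE), Version 5.0". Later in the section comes the rule for renal estimates: "Adverse event grading of toxicities related to estimated GFR should be evaluated based on the Cockcroft-Gault method or measured GFR". The sentence ends with a reference to Appendix 4 and gives neither an age range nor a unit.

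Appendix 4 is divided by age. Cockcroft-Gault stands under the heading "Patients ≥ 18 years old" and is printed in mL/min. For the rest, "Patients < 18 years old will use the Schwartz formula for the determination of creatinine clearance", printed in mL/min/1.73 m².

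Section 6.1 (Inclusion Criteria) follows the paediatric side of that division. Its creatinine limits for patients under 18 begin at age 1, and the protocol says of them: "The threshold creatinine values in this table were derived from the Schwartz formula for estimating glomerular filtration rate".

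Table 2.1 lists "Reporting of AEs, SAEs, and SUSARs" as content of the master protocol, so Section 9.2 governs each addendum that does not override it.

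**The concern.** This is a paediatric and young adult platform, yet the only estimating formula that Section 9.2 names is the one its own appendix reserves for adults. A site can apply the sentence literally and use Cockcroft-Gault in a 2-year-old, or follow the cross-reference and use Schwartz. Both choices can be defended from the text, and they give different numbers for the same child on the same day.

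The missing scale adds a second ambiguity, since the two formulas are printed in different units. The rest of the protocol does not settle it: the GFR threshold in Section 6.1, which also cites Appendix 4, is printed in mL/min/m², a unit that neither formula yields.

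What is at stake is comparability of renal toxicity grades between sites and between addenda. Those grades enter the summaries in Section 10.3.1, which cover "AEs, including severity and possible relationship to study drug".

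**Working it through.** The protocol states no figure to reproduce. The check evaluates both Appendix 4 formulas on the same child.

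**Formulas (Appendix 4; creatinine SCr in mg/dL)**

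- Cockcroft-Gault (CG) = (140 − age) × weight × (0.85 if female) / (72 × SCr), in mL/min.
- Schwartz = k × height / SCr, in mL/min/1.73 m². k is 0.55 for females and pre-adolescent males, 0.70 for adolescent males.

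**Assumptions (not in the protocol)**

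- Body sizes as tabulated below.
- Body surface area BSA = √(weight × height / 3600).
- For boys, k = 0.55 at age 10 and 0.70 at age 17.

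**Ratios.** SCr cancels, so the ratio depends only on age, sex and body size:

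- As printed: [(140 − age) × weight × (0.85 if female) / 72] / (k × height).
- Common scale: as-printed ratio × 1.73 / BSA. The result is the same whether both are put in mL/min or both per 1.73 m².

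**Worked case: boy aged 2, 12 kg, 87 cm**

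- As printed: (138 × 12 / 72) / (0.55 × 87) = 23.0 / 47.85 = 0.481.
- BSA = √(12 × 87 / 3600) = 0.539.
- Common scale: 0.481 × 1.73 / 0.539 = 1.54.
- At the Section 6.1 maximum creatinine for that age, 0.8 mg/dL:
  - CG = 138 × 12 / 57.6 = 28.8 mL/min, which is 92.4 mL/min/1.73 m².
  - Schwartz = 0.55 × 87 / 0.8 = 59.8 mL/min/1.73 m², which is 18.6 mL/min.

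On a common scale CG is the higher of the two (92.4 against 59.8, or 28.8 against 18.6). Read as printed it is the lower (28.8 against 59.8).

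**CG divided by Schwartz, all ages**

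| Age | Boy (kg, cm) | Common scale | As printed | Girl (kg, cm) | Common scale | As printed |
|---|---|---|---|---|---|---|
| 1 | 10, 76 | 1.74 | 0.46 | 9.5, 74 | 1.50 | 0.38 |
| 2 | 12, 87 | 1.54 | 0.48 | 12, 86 | 1.34 | 0.41 |
| 4 | 16, 103 | 1.36 | 0.53 | 16, 102 | 1.18 | 0.46 |
| 6 | 20.5, 115 | 1.29 | 0.60 | 20, 115 | 1.08 | 0.50 |
| 10 | 32, 138 | 1.19 | 0.76 | 32, 138 | 1.01 | 0.65 |
| 17 | 65, 176 | 0.88 | 0.90 | 55, 163 | 0.98 | 0.89 |

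**Sensitivity to body size**

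- Weight varied 15% either way, BSA recomputed, ages 1 to 6: common scale 1.00 (girl aged 6, −15%; 0.998 unrounded) to 1.87 (boy aged 1, +15%); as printed 0.33 to 0.69.
- Weight varied 20% and height 7%, both sexes, starting from one set of sizes per age (10 kg, 76 cm at age 1; 12 kg, 87 cm at age 2; 16 kg, 102 cm at age 4; 20 kg, 115 cm at age 6): common scale 1.19–2.12 at age 1, 1.06–1.89 at age 2, 0.95–1.69 at age 4 and 0.87–1.56 at age 6; as printed 0.29–0.60, 0.31–0.62, 0.34–0.70 and 0.37–0.76.

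The reversal of direction is therefore firm at ages 1 and 2. From about age 4 it holds at typical sizes but not at the extremes.

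**The case against.** The strongest reply is that Section 9.2 cites Appendix 4, and a site that follows the citation reaches the age split. On that view the sentence merely fails to mention Schwartz. This makes the repair easy but does not remove the defect: if Cockcroft-Gault applies only where the appendix assigns it, Section 9.2 names no estimating formula for anyone under 18. The option of measured GFR does not help a child who is graded on an estimate.

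Second, the grading criteria that Section 9.2 adopts may themselves fix the unit. The protocol does not reproduce them, so this cannot be checked here. If they do, the scale question closes, but the choice of formula stays open.

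Third, the as-printed ratios mix a difference of formula with a difference of indexing. That is true, and the common-scale ratios are the fair measure of the formulas alone. The as-printed figures show only what happens if the appendix outputs are used as they stand.

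Fourth, the practical effect is limited, and these limits stand:

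- No specific grade shift is shown.
- Relative change within a child of unchanged age and body size is the same under either formula, because each is a constant divided by creatinine.
- Age limits are set in the addenda, which may also override the sentence.
- Appendix 4 confines its calculation to local laboratory results.
- The creatinine table and GFR threshold in Section 6.1 govern eligibility, so they are context. The conflict itself lies between Section 9.2 and Appendix 4.

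**Conclusion.** The concern holds and should be fixed. Section 9.2 and Appendix 4 give different instructions for patients under 18 graded on an estimate, and no passage reconciles them. Read literally, Section 9.2 applies to children a formula that the protocol's own appendix reserves for adults.

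At the assumed body sizes and BSA formula, Cockcroft-Gault exceeds Schwartz by 8% to 74% at ages 1 to 6 on a common scale. If the two are used as printed, it is 40% to 62% lower. At age 17 it is 2% to 12% lower on a common scale. The problem therefore matters mainly in young children, where an addendum enrols them. It affects descriptive safety summaries and no efficacy inference.

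**What to change.** Reconcile Section 9.2 with Appendix 4 for patients under 18. One way is to replace the reference to Cockcroft-Gault with a reference to the age-specific formula in Appendix 4, keeping measured GFR as the alternative. If the sponsor intends another formula for grading in children, Section 9.2 should say so and explain the departure from Appendix 4. In either case, state whether grading uses mL/min or mL/min/1.73 m².

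The cost is one sentence in Section 9.2. Appendix 4 already contains both formulas, and no new procedure or data collection is needed.
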